5.2 Study Visits and Assessments

This will be an acute bioavailability and biomarker study that consists of 4 study visits at our clinic (**Figure 1**). Screened, eligible, and interested participants (n=5) will be asked to avoid consumption of foods rich in flavonoids for 2 weeks (i.e., washout). Prior to their baseline visit, participants will be asked to collect a 24 hour urine sample to evaluate flavonoid metabolites and to fast 12 hours prior to their scheduled visit. Fasted participants (12-hour fast) will come to our clinical research laboratory, have a baseline blood draw and be randomized to either consume a 24 g dose (equivalent to ~ 1 cup) or a 48 g dose (equivalent to ~2 cups) of freeze-dried blueberry powder. Participants will be asked to consume their assigned dose in the morning for the next 3 days, while continuing to avoid other sources of flavonoids. The participants will be recommended to consume their assigned dose or mixed with 6-8 fluid ounces of water per packet of powder. After the last dose of powder is consumed on day 3, participants will begin collecting 24 hour urine and have a follow-up fasted blood draw the following day. After a second two week wash-out period, participants will be asked to repeat the same procedure with the other dose of blueberry powder so individuals can serve as their own control. During the study, participants will also be asked to complete diet logs to explore the impact of other foods/dietary habits on flavonoid bioavailability.

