3.1 Study Objectives and Aims

Aim 1: Determine the acute bioavailability of two different doses of blueberry flavonoids in older adults. ***We hypothesize that those who consume 48 g of blueberry powder will have a higher percentage of flavonoid***

metabolite biomarkers in urine after 3 days of freeze-dried blueberry powder consumption compared to those who consume 24 g.

Aim 2: Determine the acute impact of berry flavonoids on inflammation in older adults. *We hypothesize that after 3 days of freeze-dried blueberry intake, select inflammatory biomarkers (e.g., C-reactive protein, interleukin-6, interleukin-1 beta, tumor necrosis factor alpha) will be lower compared to baseline, and those consuming the 48 g of powder will have a greater reduction. Additionally, the reductions in inflammatory markers will correlate with increases in flavonoid metabolites.*

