3.6 Study Intervention Products

Given that 100% purified anthocyanins are not commercially available, we will utilize a dietary source of anthocyanins. Blueberries are one of the richest sources of dietary anthocyanins and also conveniently concentrated with fiber. We will use freeze-dried powdered blueberries as the intervention product. The powder is packaged in 24 g amounts. Therefore, participants will be asked to consume either one or 2 packets of powder each day depending on what arm of the intervention they are on. They will be asked to consume their entire dose in the morning. Participants will be asked to consume their dose mixed with water (i.e., ~ 6-8 ounces for every packet of powder). The powder will be provided by the U.S. Blueberry Council.. See §5.3 for further information on dietary intervention.

CHAPTER 4 RECRUITMENT AND DATA COLLECTION

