Diet Records: 1-day and 3-day diet records will be filled out by participants, documenting the amount and types of foods/beverages ate during the allotted time. Records will be reviewed by research staff for accuracy and completeness. Records will be entered into a dietary analysis program (e.g., Nutrition Data System for Research) to estimate dietary intake of nutrients.

Visit 1 (1st Baseline Visit, approximately 60 minutes)

Prior to their baseline visit, individuals will be asked to also fast 12 hours prior to their scheduled visit. They will come to our clinical research laboratory, have a blood draw (up to 20 mL of plasma and/or serum) and be asked questionnaires about their lifestyle (e.g., smoking habits), current social network, sleep habits, positive/negative affect, and relevant symptoms (e.g., gastrointestinal symptoms, pain etc.). For safety depressive symptoms (via CES-D/CESD-R and PHQ-9) and suicidal ideation will be assessed (via P4SS). Height, weight, and vitals will be measured. They will turn in their 1-day diet record and their 24-hour urine sample. After participants will be randomly assigned to either consume a 24 g dose (equivalent to ~ 1 cup) or a 48 g dose (equivalent to ~2 cups) of freeze-dried blueberry powder mixed in water. Participants will be asked to consume their assigned dose in the morning for the next 3 days, while recording diet records and compliance during those 3 days. Immediately after they consume the last dose of their intervention powder (e.g., Day 3), they will begin to collect a 24 hour urine sample for the day prior to their next study visit.

Lifestyle: Alcohol use, smoking status, etc. will be collected via self-report.

Social Network: Subjective perception of social support and connectedness will be evaluated using a validated questionnaire.

Sleep Quality and Quantity: Sleep will be evaluated by a self-report questionnaire and/or sleep log diary.

Height: Height will be measured at the baseline visit using a stadiometer.

Weight: Weight will be measured using a digital Health-o-meter scale.

Vital Signs (e.g., seated blood pressure) will be measured at the baseline visit. After 3-5 minutes of rest, seated blood pressure will be measured twice with an automated cuff.

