5.3 Dietary Intervention

During this intervention participants will be asked to consume a 24 g or 48 g dose of freeze-dried blueberry powder (in a randomized order), which will be provided by the United States Highbush Blueberry Council. A 24 g portion of blueberry powder is equivalent to approximately 1 cup of fresh blueberries and contains approximately 300 mg of flavonoids, and 48 g is equivalent to approximately 2 cups of fresh blueberries and contains approximately 600 mg of flavonoids. The powder is packaged in 24 g allotments. Thus, those consuming the 24 g will be asked to consume 1 packet of powder and those consuming 48 g will be asked to consume 2 packets. Therefore, the individuals and the researchers cannot be blinded to the allocation of intervention arm. Dietary flavonoids appear well-tolerated in older adults with no apparent adverse effects.[36] However, all adverse events will be appropriately documented.

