6.1 Statistical Analysis

All analyses will be performed by intent to treat. Change in total urinary flavonoid metabolites and change in inflammatory markers will be calculated between baseline and the final follow-up (i.e., day 4 of each dosing cycle). The distribution of change in urinary flavonoid metabolites and serum inflammatory markers, will be summarized using sample quantities and kernel density estimates. Following this, formal inference and estimation of treatment effects will use a Student's paired t-test for comparison of urinary flavonoids and serum inflammatory markers between the 24 g dose and the 48 g dose. However, we will also explore other analytic methods that account for repeated measures. The correlation between changes in urinary flavonoid metabolites and changes in inflammatory markers will be assessed using scatterplot smoothing and summarized using regression analyses (linear or non-linear). Given the small sample size and pilot nature of the trial, we set a p-value threshold of 0.25 as suggestive of differences for all comparisons.[49]

We will also develop 80% confidence interval estimates of inter- and intra-individual variation (i.e., standard deviation) in these measures for sample size calculations for a subsequent clinical trial. The lower limit of the 80% CI of urinary flavonoid metabolites will provide a conservative estimate of the usual bioavailability of

flavonoids. In future studies, this lower limit will be used to estimate the amount/dose of berries needed to obtain a total urinary flavonoid metabolite concentration of ~1600 µg/mL, which coincided with the reductions in serum inflammatory marker, CRP in adults following a high-fat, high polyphenol meal challenge.

CHAPTER 7 DATA MANAGEMENT AND QUALITY

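### Mixing water scales with the number of packets, so if urinary metabolites are used as an uncorrected concentration, the 48 g versus 24 g comparison could be biased against 48 g

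*Combined protocol and SAP*

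**What the plan says.** Aim 1 in section 3.1 is to "Determine the acute bioavailability of two different doses of blueberry flavonoids in older adults". Water is tied to the packet in two places: section 3.6 gives about "6-8 ounces for every packet of powder", and section 5.2 recommends the dose be "mixed with 6-8 fluid ounces of water per packet of powder". Section 5.3 fixes the packet count: "those consuming the 24 g will be asked to consume 1 packet of powder and those consuming 48 g will be asked to consume 2".

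On timing, section 3.6 states: "They will be asked to consume their entire dose in the morning". Section 5.1 (Visit 1) continues: "Immediately after they consume the last dose of their intervention powder (e.g., Day 3), they will begin to collect a 24 hour urine sample". The baseline collection falls on the last day of washout, when there is no study drink.

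Sections 3.5 and 5.4 define the urinary outcome as an absolute pre-post change in total metabolites, without a unit. Urine is aliquoted and frozen. Recording of 24-hour volume and correction for creatinine or specific gravity are not mentioned. Section 6.1 compares the doses with a paired t-test. It then plans to use the lower 80% limit in future studies to estimate the berry dose "needed to obtain a total urinary flavonoid metabolite concentration of" about 1600 µg/mL.

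**The concern.** A comparison of two doses is cleanest when the cycles differ only in the amount of powder. Here the nominal fluid taken with the dose differs too, and it moves with dose inside every participant. Pairing within person and randomising the order therefore do not remove the difference. Subtracting baseline does not remove it either, because the baseline day carries no study water in either cycle.

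Added fluid lowers a urinary concentration even when the same mass is excreted. If excretion were truly proportional to dose, a diluted 48 g sample would look like absorption levelling off at the higher dose. That is close to the question the pilot is meant to inform, and the concentration scale in section 6.1 would carry the distortion into later dose setting.

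**Working it through.** The plan states no urine volume, effect size, SD or power, so there is no figure of its own to reproduce. The check sizes the dilution.

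**Inputs from the documents**
- Water: 6-8 fl oz per packet (3.6, 5.2). Packets: 1 at 24 g, 2 at 48 g (5.3).
- Whole dose in the morning (3.6); collection starts right after the Day 3 dose (5.1).

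**Assumptions not in the documents**
- 24-hour urine volume V of 1-2 L in the 24 g cycle.
- All the extra water is excreted within the collection and is not offset by drinking less at other times.
- Excreted mass doubles with dose.

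**Step 1, study water (1 fl oz = 29.57 mL)**
- 24 g: 6-8 oz = 177-237 mL.
- 48 g: 12-16 oz = 355-473 mL.
- Extra at 48 g: 177-237 mL. The ratio is 2 at equal ounces per packet. It is 1.5 (12/8) to 2.67 (16/6) if the ounces per packet differ between cycles.

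**Step 2, dilution factor f = V / (V + extra)**
- V = 1000 mL, extra 237 mL: f = 1000/1237 = 0.81.
- V = 2000 mL, extra 177 mL: f = 2000/2177 = 0.92.

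The 48 g concentration is then 8-19% too low.

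**Step 3, observed ratio = 2 × f**
- 2 × 0.809 = 1.62 and 2 × 0.919 = 1.84, against a true 2.0.

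**Step 4, difference scale, which the paired t-test uses**
- Set the 24 g increment to 1 and background to zero. The true 48-minus-24 contrast is 1 and the observed contrast is 2f − 1 = 0.62-0.84, a shrinkage of 16-38%.
- Background excretion makes the shrinkage larger, because background is diluted too. The documents give no background level.

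**Step 5, sensitivity**
- Half the extra water offset: extra = 89-118 mL, f = 0.89-0.96, ratio 1.79-1.92.
- All of it offset: f = 1, no bias.
- V defined without any study water and taken as 1.0-2.5 L, with w the water per packet: factor (V + w)/(V + 2w) = 0.84-0.94, ratio 1.68-1.88. Same direction, similar size.
- Outcome as mass per 24 hours (concentration × volume): volume cancels, no dilution bias.

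**The case against.** The strongest reply is that the harm depends on a scale the plan never adopts for its primary comparison. A timed 24-hour collection naturally supports total excretion. The Aim 1 hypothesis speaks of a percentage of metabolites, and Chapter 2 describes bioavailability as the fraction of flavonoids absorbed; if that means recovery relative to dose, it needs mass and water is irrelevant. The 1600 µg/mL figure is a target for later studies and is not attached to the t-test. This stands, and it makes the point conditional. It does not remove the point, because no unit is stated for the outcome, no volume is said to be recorded, and the one urinary unit given is a concentration that feeds a stated dose-setting step.

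The water is also only recommended and other fluid is free, so dilution at 48 g is an inference. That stands too: with full compensation the effect is nil. Diet records capture beverages, but section 6.1 plans no adjustment for fluid, and five participants leave little room for one.

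A reader might infer two stronger things. The first is that every concentration-based result is biased. The inflammatory markers are measured in serum from a fasted draw the next day, and an argument about urine dilution does not reach them. The second is a quantified loss of power. The plan gives no effect size, SD or power to start from, and dilution would alter the spread of the 48 g values as well as their mean, so no power loss should be quoted.

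**Conclusion.** The concern holds in conditional form. The nominal fluid difference of 177-237 mL/day and its place inside the Day 3 collection follow directly from the text. Whether it biases the result depends on the urinary scale and on how participants drink otherwise. If metabolites are analysed, or carried forward, as an uncorrected concentration, the comparison could be biased against 48 g, with a true 2.0-fold ratio reading about 1.62-1.84 under the assumptions listed. This is an avoidable, dose-linked difference that is cheap to remove. It does not show that the planned primary comparison is biased.

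**What to change.** In sections 3.6 and 5.2 and in the participant instructions, replace the per-packet water rule with one total volume of water taken with the dose, the same in both cycles. The investigators choose the volume, and the amount of powder is unchanged.

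As a companion, state in sections 3.5, 5.4 and 6.1 that the 24-hour urine volume is recorded and that total metabolites are analysed as mass per 24 hours. This also removes dilution from all other fluid intake, which equal mixing water alone would leave. Volume must be measured before aliquoting, because it cannot be recovered later.

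The cost is a few sentences and one volume reading per collection, with no added visits or samples. The small downside is more plain water in the 24 g cycle or a thicker drink in the 48 g cycle.

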5.3 Dietary Intervention

During this intervention participants will be asked to consume a 24 g or 48 g dose of freeze-dried blueberry powder (in a randomized order), which will be provided by the United States Highbush Blueberry Council. A 24 g portion of blueberry powder is equivalent to approximately 1 cup of fresh blueberries and contains approximately 300 mg of flavonoids, and 48 g is equivalent to approximately 2 cups of fresh blueberries and contains approximately 600 mg of flavonoids. The powder is packaged in 24 g allotments. Thus, those consuming the 24 g will be asked to consume 1 packet of powder and those consuming 48 g will be asked to consume 2 packets. Therefore, the individuals and the researchers cannot be blinded to the allocation of intervention arm. Dietary flavonoids appear well-tolerated in older adults with no apparent adverse effects.[36] However, all adverse events will be appropriately documented.

5.4 Outcome Measures

The primary outcomes of this study are urinary flavonoid metabolite biomarkers (i.e., a marker of flavonoid bioavailability) and inflammatory biomarkers described below:

Flavonoid Biomarkers: Ingested flavonoids typically undergo extensive metabolism before and after absorption into circulation. Very little of the parent flavonoid structures (e.g., cyanidins) are absorbed intact, while the rest of the parent flavonoids are either extensively metabolized in the enterocyte or by

the gut microbiota into phenolic acids (e.g., hippuric acid, homovanillic acid, feurlic acid etc).[37-40] These phenolic acids are thought to be the active metabolites that are primarily responsible for the biologic effects of flavonoids.[41, 42] While these phenolic metabolites are in circulation, they are subject to further metabolism. Due to the extensive and complex metabolism that happens in circulation, most studies opt to use urine samples to evaluate bioavailability since select phenolic acids (primarily hippuric acid) appear to be the final metabolic end product of flavonoid metabolism.[43] It is estimated that approximately 50 major parent flavonoids and metabolites are detected in urine after ingestion of blueberries,[44] which have a moderate degree of inter- and intra-individual variability.[45] This high degree of variation is likely due to differences in lifestyle factors,[46] as well as biology/physiology between individuals. The bioavailability of total flavonoid biomarkers will be evaluated by absolute change in total flavonoid urinary metabolites. Participants will be asked to collect a 24 hour urine sample before and after powder consumption. Urine will be aliquotted and stored at -80 degrees C until analysis. Following the intervention period, frozen urine will be shipped overnight in bulk to a reputable lab (e.g., the Metabolomics and Analytical Chemistry Research Core at the University of Arkansas for Medical Sciences) where flavonoids and their flavonoid metabolic biomarkers are measured regularly. Urinary flavonoids and their metabolites will be measured by High-Performance Liquid Chromatography-Tandem Mass Spectrometry, as previously described.[47] The total flavonoid/metabolites pre- and post-intervention will be calculated for each participant.

Inflammatory Biomarkers: Given that it will take several hours for the flavonoids to reach the gut microbiota for metabolism and production of the active metabolites (i.e., phenolic acids), an acute 3-day feeding study was chosen to ensure enough time for 1) the metabolites to be formed via gut microbes and 2) a chance to modulate regulation of cytokine production. A panel of several serum inflammatory markers including interferon gamma, interleukins 1B, 6, 8, and 10, and tumor necrosis factor alpha) will be measured using a commercially available Luminex (R&D Systems, Minneapolis MN) bead-based immunoassay that allows for multiplex detection of several analytes in one sample. The Luminex will have ample sensitivity of the aforementioned markers range from 0.40-1.8 pg/mL, given that serum levels of the markers are typically >10 pg/mL.[48] C-reactive protein (CRP) will be measured using a commercially available high-sensitivity enzyme-linked immunoassay (ELISA, R&D Systems, Minneapolis MN) and will be our primary marker to reflect inflammation. The CRP ELISA has a sensitivity of 0.02 ng/mL which will be sufficient given that typically depressed individuals have levels >2 mg/mL.[48] The Luminex and ELISA will be performed by a reputable lab (e.g., our collaborators at the University of Connecticut). Pre-, post-intervention change in all measured inflammatory biomarkers will be calculated for each participant. All of the inflammatory biomarkers that will be measured have been previously linked with depressive symptoms,[48] and will thus be relevant to our recruited population.

CHAPTER 6. STATISTICAL DESIGN

6.1 Statistical Analysis

All analyses will be performed by intent to treat. Change in total urinary flavonoid metabolites and change in inflammatory markers will be calculated between baseline and the final follow-up (i.e., day 4 of each dosing cycle). The distribution of change in urinary flavonoid metabolites and serum inflammatory markers, will be summarized using sample quantities and kernel density estimates. Following this, formal inference and estimation of treatment effects will use a Student's paired t-test for comparison of urinary flavonoids and serum inflammatory markers between the 24 g dose and the 48 g dose. However, we will also explore other analytic methods that account for repeated measures. The correlation between changes in urinary flavonoid metabolites and changes in inflammatory markers will be assessed using scatterplot smoothing and summarized using regression analyses (linear or non-linear). Given the small sample size and pilot nature of the trial, we set a p-value threshold of 0.25 as suggestive of differences for all comparisons.[49]

We will also develop 80% confidence interval estimates of inter- and intra-individual variation (i.e., standard deviation) in these measures for sample size calculations for a subsequent clinical trial. The lower limit of the 80% CI of urinary flavonoid metabolites will provide a conservative estimate of the usual bioavailability of

flavonoids. In future studies, this lower limit will be used to estimate the amount/dose of berries needed to obtain a total urinary flavonoid metabolite concentration of ~1600 µg/mL, which coincided with the reductions in serum inflammatory marker, CRP in adults following a high-fat, high polyphenol meal challenge.

CHAPTER 7 DATA MANAGEMENT AND QUALITY

7.1 Data Management Plan

All data collected for analysis will be de-identified and assigned a unique study number. Any data collected on paper forms will be kept in a locked file cabinet at HRC. Data collected on paper forms will be entered and stored on a password-protected secure server at HRC. When possible, data will be collected directly via our electronic data capture system (e.g., REDCap).

The Institute for Aging Research primarily employs the REDCap system to facilitate data management operations. REDCap is a full-featured clinical trials data management system (DMS) accessible to data entry and data analysis workstations using secure Web technologies. The REDCap product is developed and maintained by Vanderbilt University in cooperation with REDCap Consortium members, including HRC. HSL hosts and maintains a dedicated instance of REDCap for use across our research enterprise. Each research study is provided separate project workspace in which all of the study data are stored in a MySQL relational database on the private corporate network behind several firewalls and located physically within the HSL data center.

7.2 Participant Tracking

Each recruited participant will be tracked closely throughout study enrollment. If desired, a study events calendar will be created for each participant. Any outstanding or incomplete visits will be accessible in real time to the project director and study team. The study team will maintain regular communications with each study participant throughout enrollment, through regularly scheduled follow up calls, and established retention strategies will be used.

CHAPTER 8 DATA SAFETY MONITORING PLAN

